7.4. Gilead Reporting Requirements

Depending on relevant local legislation or regulations, including the applicable US FDA Code of Federal Regulations, the EU Clinical Trials Directive (2001/20/EC) and relevant updates, and other country-specific legislation or regulations, Gilead may be required to expedite to worldwide regulatory agencies reports of SAEs, serious adverse drug reactions (SADRs), or suspected unexpected serious adverse reactions (SUSARs). In accordance with the EU Clinical Trials Directive (2001/20/EC), Gilead or a specified designee will notify worldwide regulatory agencies and the relevant IEC in concerned Member States of applicable SUSARs as outlined in current regulations.

Assessment of expectedness for SAEs will be determined by Gilead using reference safety information specified in the investigator's brochure.

All investigators will receive a safety letter notifying them of relevant SUSAR reports associated with any study IMP. The investigator should notify the IRB or IEC of SUSAR reports as soon as is practical, where this is required by local regulatory agencies, and in accordance with the local institutional policy.

7.5. Clinical Laboratory Abnormalities

Laboratory abnormalities are usually not recorded as AEs or SAEs. However, laboratory abnormalities (eg, clinical chemistry, hematology, coagulation, and urinalysis) independent of the underlying medical condition that require medical or surgical intervention or lead to investigational medicinal product interruption or discontinuation must be recorded as an AE, as well as an SAE, if applicable. In addition, laboratory or other abnormal assessments (eg, electrocardiogram, X-rays, vital signs) that are associated with signs and/or symptoms must be recorded as an AE or SAE if they meet the definition of an AE (or SAE) as described in Sections 7.1.1 and 7.1.2. If the laboratory abnormality is part of a syndrome, record the syndrome or diagnosis (ie, anemia) not the laboratory result (ie, decreased hemoglobin).

Severity should be recorded and graded according to the Common Terminology Criteria for Adverse Events (CTCAE) and Laboratory Abnormalities. For AEs associated with laboratory abnormalities, the event should be graded on the basis of the clinical severity in the context of the underlying conditions; this may or may not be in agreement with the grading of the laboratory abnormality.

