Reference Therapy, Dose, and Mode of Administration:	PTM Filgotinib (1 tablet) administered orally once daily in the AM PTM GS-9876 (1 tablet) administered orally once daily in the AM
Criteria for Evaluation:	
Safety:	Safety will be assessed during the study through the reporting of AEs, clinical laboratory tests, vital sign assessments, physical examinations findings, and ECGs. Treatment emergent AEs including infection, worsening of proteinuria, or decrease in eGFR will be of particular interest.
Efficacy:	
Primary Endpoint
 
• The percent change in urine protein from Baseline (Day 1) to Week 16 (assessed by urine protein excretion during a 24-hour urine collection). 
Secondary Endpoints
 
• Change from Baseline (Day 1) in urine protein (assessed by urine protein excretion during a 24-hour urine collection) at Week 16• Change from Baseline (Day 1) in eGFR at Week 16• Change from Baseline (Day 1) in UPCR (assessed by urine protein excretion during a 24-hour urine collection) at Week 16• Proportion of subjects with partial remission (defined as urine protein excretion below < 3 g/d and urine protein excretion decrease by ≥ 50% among subjects with Baseline (Day 1) nephrotic range proteinuria [urine protein excretion ≥ 3 g/d]; or urine protein excretion decrease by ≥ 50% among subjects with subnephrotic range proteinuria [urine protein excretion < 3 g/d]) at Week 16• Proportion of subjects with complete remission (defined as urine protein excretion below 0.5 g/day, with no hematuria) at Week 16
Biomarker Endpoints	
• Change in JAK-STAT-, SYK-, and disease-related biomarkers in peripheral blood and urine

- Association of changes in peripheral blood and urine biomarkers with clinical outcomes
- Association of Baseline markers with disease severity and response to filgotinib and GS-9876

Pharmacokinetics: Plasma concentrations of GS-9876, filgotinib and an active filgotinib metabolite, GS-829845, will be analyzed. Urine concentrations of GS-9876, filgotinib, and GS-829845 may be analyzed.

Statistical Methods:	Analysis Methods:

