 - d) Aspartate aminotransferase (AST) or alanine aminotransferase (ALT) > 3 times the upper limit of normal range (ULN) AND total bilirubin $> 2 \times$ ULN or accompanied by symptoms consistent with hepatic injury¹
 - e) AST and/or ALT elevations $> 3 \times$ ULN accompanied by elevated international normalized ratio (INR)¹
 - f) AST or ALT $> 5 \times$ ULN¹
 - g) Estimated glomerular filtration rate (eGFR_{MDRD}) < 40 mL/min/1.73 m² based on the MDRD formula

Subjects who discontinue study drug dosing at any time may continue with study visits, procedures, and assessments, if deemed medically appropriate by the investigator, but will not be eligible for entering the 20-week Extended Blinded Treatment Phase. Subjects who permanently discontinue study medication for any reason will not be replaced. Subjects withdrawing from the study should complete the early termination (ET) and Final FU visits. Subjects are free to withdraw from the study at any time without providing reason(s) for withdrawal and without prejudice to further treatment. The reason(s) for withdrawal will be documented in the electronic case report form (eCRF).

¹ In each case, there is a need for additional investigations, such as review of ethanol, recreational drug and dietary supplement consumption; testing for acute hepatitis A, B or C infection and biliary tract imaging should be promptly discussed with the study medical monitor.

Reasonable efforts will be made to contact subjects who are lost to follow-up. All contacts and contact attempts must be documented in the subject's file.

The sponsor has the right to terminate the study at any time in case of safety concerns or if special circumstances concerning the study medication or the company itself occur, making further treatment of subjects impossible. In this event, the investigator(s) and relevant authorities will be informed of the reason for study termination.

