7. ADVERSE EVENTS AND TOXICITY MANAGEMENT

7.1. Definitions of Adverse Events, Adverse Reactions, and Serious Adverse Events

7.1.1. Adverse Events

An adverse event (AE) is any untoward medical occurrence in a clinical study subject administered a medicinal product, which does not necessarily have a causal relationship with the treatment. An AE can therefore be any unfavorable and/or unintended sign, symptom, or disease temporally associated with the use of a medicinal product, whether or not considered related to the medicinal product. AEs may also include pre- or post-treatment complications that occur as a result of protocol specified procedures, lack of efficacy, overdose, drug abuse/misuse reports, or occupational exposure. Preexisting events that increase in severity or change in nature during or as a consequence of participation in the clinical study will also be considered AEs.

An AE does not include the following:

- Medical or surgical procedures such as surgery, endoscopy, tooth extraction, and transfusion. The condition that led to the procedure may be an adverse event and must be reported.
- Pre-existing diseases, conditions, or laboratory abnormalities present or detected before the screening visit that do not worsen
- Situations where an untoward medical occurrence has not occurred (eg, hospitalization for elective surgery, social and/or convenience admissions)
- Overdose without clinical sequelae (see Section 7.7)
- Any medical condition or clinically significant laboratory abnormality with an onset date before the consent form is signed and not related to a protocol-associated procedure is not an AE. It is considered to be pre-existing and should be documented on the medical history CRF.

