7.1.6. Summaries of Adverse Events and Deaths

Treatment-emergent AEs will be summarized based on the Safety Analysis Set. The tables will be presented by treatment period.

A brief, high-level summary of the number and percentage of subjects who experienced at least 1 TEAE in the categories described below will be provided by treatment group. All deaths observed in the study will also be included in this summary.

The number and percentage of subjects who experienced at least 1 TEAE will be provided and summarized by SOC, PT, severity and treatment group for the following:

- All TEAEs
- All TE treatment-related AEs
- All TE SAEs
- TEAEs of interest

For the AE categories described below, summaries will be provided by SOC, PT, and treatment group:

- TEAEs of Grade 3 or higher (by maximum severity)
- TE treatment-related AEs of Grade 3 or higher (by maximum severity)
- All TE treatment-related SAEs
- All TEAEs leading to premature discontinuation of study drug
- All TEAEs leading to premature discontinuation of study

Multiple events will be counted only once per subject in each summary. Adverse events will be summarized and listed first in alphabetic order of SOC and then by PT in descending order of total frequency within each SOC. For summaries by severity grade, the most severe grade will be used for those AEs that occurred more than once in an individual subject during the study.

In addition, data listings will be provided for the following:

- All AEs, indicating whether the event is treatment emergent
- SAEs
- Deaths
- AEs leading to premature discontinuation of study drug or study
- TEAEs of interest

Adverse events of interest will be identified by the use of either Standardized MedDRA queries or MedDRA search terms.

The following adverse events of interest will be presented:

- All infections (defined as all PTs within the Infections and Infestations SOC)
- Serious infections (defined as all PTs within the Infections and Infestations SOC that are SAEs)
- Herpes Zoster infection
- Opportunistic infections
- Active tuberculosis
- Hepatitis B and C

- Serious Major Adverse Cardiovascular Events (MACE)

Unstable angina

Cardiac failure

Stroke

Transient ischemic attack

Percutaneous coronary intervention

Myocardial Infarction

- Gastrointestinal perforation
- Venous thrombotic events and pulmonary embolism
- Malignancy including non-melanoma skin cancer
- Transaminases increased

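### Protocol Section 7.5 can be read to keep a renal decline blamed on LMN off the AE form even when it stops study drug, contradicting Sections 7.1.1 and 7.3 and the synopsis

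*Protocol*

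**What the plan says.** **Recording rule (Protocol 7.5).** The default is that "Laboratory abnormalities are usually not recorded as AEs or SAEs". One exception covers abnormalities "independent of the underlying medical condition that require medical or surgical intervention or lead to investigational medicinal product interruption or discontinuation must be recorded"; the entry is an AE, and an SAE too where that applies. A second exception lacks the qualifier: abnormal assessments "that are associated with signs and/or symptoms must be recorded as an AE or SAE if they meet the definition of an AE". A third instruction is to record the syndrome or diagnosis, rather than the laboratory result, when the abnormality is part of one.

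**General AE definition (Protocol 7.1.1).** "Preexisting events that increase in severity or change in nature during or as a consequence of participation in the clinical study" count as AEs. What is excluded is pre-existing disease and "laboratory abnormalities present or detected before the screening visit that do not worsen". Section 7.3 then requires every AE after the first dose to be reported, whatever its cause or relationship to drug.

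**Safety focus (Protocol synopsis, Criteria for Evaluation).** "Treatment emergent AEs including infection, worsening of proteinuria, or decrease in eGFR will be of particular interest".

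**Renal stop (Protocol 3.5.2, item g).** A confirmed eGFR below 40 mL/min/1.73 m², "based on the MDRD formula", leads to discontinuation of study drug.

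**Analysis (SAP 7.1.6).** One of the planned tables is "All TEAEs leading to premature discontinuation of study drug".

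**The concern.** In a subject with LMN, a drug effect on the kidney and progression of the disease can look the same. A rule that makes AE recording depend on whether the investigator blames the underlying condition asks for a judgement that often cannot be made in one person, and lets that judgement decide whether the event reaches the AE tables at all.

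The protocol makes attribution to LMN easy. Section 6.11 sets up an unscheduled visit for exacerbation of LMN and describes it as worsening proteinuria, a fall in eGFR, or both. The two renal changes that the synopsis wants watched as treatment-emergent AEs are thus labelled in advance as the underlying disease.

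At stake is whether the AE tables show study drug stops caused by falling eGFR, and whether two sites would handle the same event in the same way.

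**Working it through.** The plan states no figure to reproduce. The check is to follow one case through the passages: an asymptomatic fall in eGFR to below 40, confirmed on retest, attributed to LMN, with study drug stopped under 3.5.2(g).

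**Step 1: is it an AE under each passage?**

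| Passage | Is the case recorded as an AE? |
|---|---|
| 7.5, first exception, qualifier read as *unrelated to* | Not required; the default (usually not recorded) applies |
| 7.5, first exception, qualifier read as *regardless of* | Required |
| 7.5, signs or symptoms | Not triggered; the case is asymptomatic |
| 7.5, syndrome or diagnosis | Says which term to enter, not whether the event is an AE |
| 7.1.1 | Yes; a pre-existing condition has worsened, and the exclusion covers only what does not worsen |
| 7.3 | Cause is no ground for leaving an AE out |
| Synopsis, safety criteria | Treats a decrease in eGFR as a treatment-emergent AE |

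The qualifier follows directly after the noun it limits, so *unrelated to* is the more natural reading. That reading conflicts with the last three rows; the other agrees with them.

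**Step 2: does anything settle the conflict?** Section 7.6 says that Section 3.5 takes precedence and that the more conservative criteria apply where there is a discrepancy, but this governs toxicity management, not recording. Section 7.3 refers sites to the eCRF completion guideline, which is not among the documents.

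**Step 3: can the case arise?** The eGFR entry limit is at least 40 (Protocol 4.2, criterion 5) and the stopping limit is below 40, a gap of 40 − 40 = 0. As an illustration only, a subject entering at 42 reaches the limit after a fall of (42 − 40)/42 = 4.8%. No baseline eGFR distribution is given, so this shows that the case is plausible, not how frequent it is.

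**Step 4: where would the event be missing, and where would it still appear?**
- *Missing:* the TEAE tables and the table of TEAEs leading to study drug discontinuation. The definition in SAP 7.1.5.1 counts only events already recorded as AEs.
- *Still present:* study drug discontinuation with reasons, overall and by period (SAP 4.1); absolute and relative changes by visit for the secondary endpoints, which include eGFR, 24-hour urine protein and UPCR (SAP 6.2.1 and 6.2.2); treatment-emergent graded abnormalities by laboratory test (SAP 7.2.2.2); and the laboratory listings (SAP 7.2.1).

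**Step 5: weight of one omitted event.** One subject is 1/16 = 6.25% of a planned arm. Nine subjects were enrolled (SAP 1). The split is not stated; assuming 4 and 5, one subject is 1/5 = 20% to 1/4 = 25% of an arm. These are the sizes of a single omission, not estimates of how many there are.

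**The case against.** The strongest reply is that the protocol, taken as a whole, leans towards recording. Section 7.1.1 lists lack of efficacy among the things an AE may include and excludes pre-existing conditions only if they do not worsen. Section 7.2.1 says that ineffective treatment is not to be judged causally related, which implies that disease worsening can be entered and its attribution handled in the causality field. The unscheduled visit in Section 6.11 covers this very situation and instructs sites to review and record all AEs. If *independent of* means *regardless of*, there is no gap at all, and the eCRF guideline may say so.

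This stands in part. It shows that the protocol contradicts itself rather than clearly exempting renal decline. It does not remove the problem: Section 7.5 is the specific rule for laboratory values, so a site can reasonably follow it, and the instruction in 6.11 to record AEs does not say whether a laboratory-only change is one.

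Three stronger readings are tempting and fail:
- A reader might infer that 7.5 is the only route to an AE entry. It is not: abnormalities with signs or symptoms have their own route, without the qualifier.
- A reader might infer that the renal safety signal is lost. The documents do not support this, because the renal values and the discontinuation reasons are reported outside the AE tables.
- A reader might infer that SAP 7.2.1, by dropping descriptive laboratory statistics, leaves no renal summary. Changes in eGFR and urine protein are summarised as secondary endpoints, and graded laboratory abnormalities are tabulated.

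**Conclusion.** Wrong as written: the recording rules contradict each other. On the more natural reading of its qualifier, Section 7.5 does not require an AE entry for an asymptomatic renal change attributed to LMN, even when that change stops study drug. The synopsis, Section 7.1.1 and Section 7.3 point the other way, and no passage says which prevails.

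The consequence is limited but real. A renal stop could be absent from the TEAE tables and from the table of TEAEs leading to discontinuation, while the stop and the values behind it appear elsewhere in the report. The same event could also be recorded at one site and not at another. The frequency cannot be estimated from the documents.

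The conclusion assumes that the change is asymptomatic, that the investigator attributes it to LMN, and that the unseen eCRF guideline does not already settle the wording. The absence of a renal item from the SAP 7.1.6 list of AEs of interest is a separate gap; that list can group only what sites have recorded.

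**What to change.** Reconcile Protocol 7.5 with 7.1.1, 7.3 and the synopsis by replacing the qualifier with *regardless of suspected cause, including LMN*, and carry the same wording into the eCRF completion guideline. Suspected cause then belongs in the causality assessment and no longer decides whether an entry is made. The edit changes no dose, stopping rule or treatment.

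Because enrolment has stopped, a wording change now has limited reach. Therefore also compare every recorded eGFR-based study drug stop with the AE data before database finalization, query the site where no AE entry matches, and report in the CSR any stop that remains unmatched. This is best done while the study is still blinded; SAP 2.2 breaks the blind only after the data have been cleaned and finalized.

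The cost is one phrase in the protocol and guideline, a reconciliation covering nine enrolled subjects, and a few more AE entries for disease worsening.

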7.6. Toxicity Management

All clinical and clinically significant laboratory toxicities will be managed according to uniform guidelines detailed in [Appendix 3](#) and as outlined below.

For study-specific interruption and discontinuation criteria, refer to Section [3.5](#). Specific toxicity discontinuation criteria in Section [3.5](#) supersede below general toxicity guidelines, and in general, where discrepancy is present, the more conservative criteria apply.

The Gilead Medical Monitor should be consulted prior to study drug discontinuation when medically feasible.

7.6.1. Grades 1 and 2 Laboratory Abnormality or Clinical Event

For Grades 1 and 2 laboratory abnormalities or clinical events not specified in Section [3.5](#), continue study drug at the discretion of the investigator.

7.6.2. Grades 3 Laboratory Abnormality or Clinical Event

For Grade 3 laboratory abnormalities or clinical events not specified in Section [3.5](#), the following toxicity management guidelines apply:

- For a Grade 3 clinically significant laboratory abnormality or clinical event, IMP may be continued if the event is considered to be unrelated to IMP.
- For a Grade 3 clinical event, or clinically significant laboratory abnormality confirmed by repeat testing, that is considered to be related to IMP, IMP should be withheld until the toxicity returns to \leq Grade 2.
- If a laboratory abnormality recurs to \geq Grade 3 following re-challenge with IMP and is considered related to IMP, then IMP should be permanently discontinued and the subject managed according to local clinical practice. Recurrence of laboratory abnormalities considered unrelated to IMP may not require permanent discontinuation and study drug may be continued at the discretion of the investigator.

7.6.3. Grades 4 Laboratory Abnormality or Clinical Event

For Grade 4 laboratory abnormalities or clinical events not specified in Section [3.5](#), the following toxicity management guidelines apply:

- For a Grade 4 clinical event or clinically significant (confirmed) laboratory abnormality, study drug should be permanently discontinued and the subject managed according to local practice. The subject should be followed as clinically indicated until the laboratory abnormality returns to baseline or is otherwise explained, whichever occurs first. A clinically significant Grade 4 laboratory abnormality that is not confirmed by repeat testing should be managed according to the algorithm for the new toxicity grade.

- Study drug may be continued without dose interruption for a clinically non-significant Grade 4 laboratory abnormality (eg, Grade 4 creatine kinase after strenuous exercise or nonfasting triglyceride elevation that can be medically managed) or a clinical event considered unrelated to the study drug(s).

Grade 4 treatment-emergent toxicities will be noted by the investigator and brought to the attention of the Gilead Sciences Medical Monitor, who will discuss with the investigator and determine the appropriate course of action. All subjects experiencing AEs must be monitored periodically until symptoms subside, any abnormal laboratory values have resolved or returned to baseline levels or they are considered irreversible, or until there is a satisfactory explanation for the changes observed.

Histologic hemorrhage and thrombosis have been observed in cynomolgus monkeys that received GS-9876 at doses \geq 20 mg/kg/day. The clinical relevance of these findings to humans is unknown; these adverse events have not been reported in clinical studies of GS-9876. Any treatment-emergent adverse event involving significant bleeding or thrombosis is to be reported to the investigator and brought to the attention of the Gilead Sciences medical monitor, or designee, to discuss the appropriate course of action.

Any questions regarding toxicity management should be directed to the Gilead Sciences Medical Monitor.

7.7. Special Situations Reports

7.7.1. Definitions of Special Situations

Special situation reports include all reports of medication error, abuse, misuse, overdose, reports of AEs associated with product complaints, occupational exposure with an AE, pregnancy reports (regardless of an associated AE), and an AE in an infant following potential exposure from breastfeeding.

Medication error is any unintentional error in the prescribing, dispensing, or administration of a medicinal product while in the control of the health care provider, subject, or consumer.

Abuse is defined as persistent or sporadic intentional excessive use of a medicinal product by a subject.

Misuse is defined as any intentional and inappropriate use of a medicinal product that is not in accordance with the protocol instructions or the local prescribing information.

An overdose is defined as an accidental or intentional administration of a quantity of a medicinal product given per administration or cumulatively which is above the maximum recommended dose as per protocol or in the product labelling (as it applies to the daily dose of the subject in question). In cases of a discrepancy in drug accountability, overdose will be established only when it is clear that the subject has taken the excess dose(s). Overdose cannot be established when the subject cannot account for the discrepancy except in cases in which the investigator has reason to suspect that the subject has taken the additional dose(s).

Product complaint is defined as complaints arising from potential deviations in the manufacture, packaging, or distribution of the medicinal product.

Occupational exposure is defined as exposure to a medicinal product as a result of one's professional or non-professional occupation.

